While the treatment strategies for PAH are undergoing a paradigm shift away from vasoactive drugs towards tackling the structural remodeling of the pulmonary vasculature, vasodilators still maintain a central position in the currently available treatment modalities. Often, drugs that target different pathways leading to pulmonary vasodilation are administered concomitantly for better effect, especially in patients with group 1 PAH. These drugs include orally administered calcium channel blockers, endothelin receptor blockers and phosphodiesterase-5 inhibitors. J32-adrenergic agonists are potent vasodilators and could be administered by inhalation as add-ons to currently used oral vasodilators in patients with group 1 PAH. Thus far, this possibility has not been explored in this population.

We have previously reported that the short acting J32-adrenergic agonist albuterol, administered by inhalation, markedly and significantly reduced PVR in lung-and heart healthy current smokers and never smokers (1). Other studies involving inhaled J32- adrenergic agonists were carried out in patients with COPD without or with PAH (group 3). Early studies have shown that short-acting J32-adrenergic agonists can reduce PVR in hypoxic COPD patients with PAH (2,3). More recently, Cazzola et al (4) assessed two long-acting J32-adrenergic agents (formoterol and salmeterol) in COPD patients, with or without mild pulmonary hypertension. Following administration of these agents, they observed a reduction in echocardiographic systolic pulmonary arterial pressure that lasted less than 180 min, with a trough minimizing between 15 min and 60 min. It is difficult to separate direct from indirect vasodilation in these studies, i.e. did the J32-adrenergic agonists have a direct effect on the pulmonary circulation or an indirect effect by improving airway function. This caveat also applies to another investigation of albuterol's action in patients with PAH in whom the drug caused both bronchodilation and pulmonary vasodilation at the time of right heart catheterization to assess responses to vasodilators, with the possibility that a change in ventilation/perfusion relationship reversed hypoxic vasoconstriction thereby lowering pulmonary arterial pressure (5).

The purpose of the present pilot study is to test the hypothesis that in patients with group 1 PAH who are on regular oral pulmonary vasodilator

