therapy, inhaled albuterol causes transient pulmonary vasodilation. If the results support this premise, they could serve as the basis for a phase 2 trial investigating the potential for using inhaled long-acting 2-adrenergic agonists as add-on therapy in group 1 PAH.

'Research Plan

Test subjects

Ten patients (males and females) over the age of 18 years with group 1 PAH will be enrolled on the study. Participants will be recruited from the University of Miami Pulmonary Hypertension Clinic under the direction of [name] [name], a co-investigator.

Inclusion criteria

- A MPAP >25mmHg, PVR>3 wood/units and pulmonary arterial wedge pressure 15mmHg, as documented by right heart catheterization within the last 3 years
- Regular use of oral pulmonary vasodilators

Exclusion criteria

- Presence of chronic respiratory disease (as documented by prior lung imaging and pulmonary function tests), cardiovascular disease (as documented by prior echocardiography and/or left heart catheterization), thromboembolic PAH (as documented by pulmonary angiography)
- women of childbearing potential who do not use accepted birth-control measures
- pregnant and breast-feeding women (vide infra)
- respiratory infection within 4 weeks of testing
- A systemic systolic arterial BP> 150 and/or diastolic arterial BP>100 on the experiment day
- A resting O₂ saturation of< 90%
- Current smoking
- BMI >35 kg/m² and/or a diagnosis of obstructive sleep apnea
- Use of inhaled or intravenous pulmonary vasodilators

Targeted outcomes

Change in MPAP, PVR after inhalation of 270µg albuterol administered with a spacer. These parameters, measured/calculated by echocardiography, will be obtained before and at 15, 30, 60 and 120 after albuterol or placebo inhalation. At each measurement point, systemic blood pressure, O₂ saturation by pulse oximetry and spirometry will also be measured (the latter to rule out drug induced changes in airway function that could indirectly influence pulmonary hemodynamics). We previously have observed that the albuterol response wanes by 60 min in healthy subjects (1). Each participant will serve as his/her own control and the two treatments will be administered on different experiment days in random order. Participants and investigators will be blinded (HFA albuterol and matching placebo are available to the investigators).

Measurements

Echocardiography and calculation of PVR:

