The study is a repeated-measures design with medication treatment vs. placebo and time post-treatment (pre-inhalation baseline, 15, 30, 60, 120min) as fixed within subject effects. The resulting factorial combinations will permit ANCOVA estimation of the main effects of treatment and time, as well as the 2-way interaction (treatment by time). In addition, ANCOVA analyses will be performed to examine treatment effects on the different outcomes. Significance will be accepted at $p < 0.05$.

Procedures

There will be 3 study assessment visits per participant, including the screening visit to confirm study eligibility. Visits 2 and 3 will commence about 9am. The subjects will be asked to keep taking their usual oral pulmonary vasodilator on the experiment days.

Visit 1

On this screening visit, after the subjects have signed an informed consent and HIPAA forms, a medical history will be obtained and then a physical examination will be administered. If they meet screening entry criteria, they will undergo spirometry and the determination of O₂ saturation, blood pressure and heart rate. If the subjects still meet entry criteria, they will be invited to return for visit 2.

Visit 2 and Visit 3

Echocardiographic measurements will be made before and at 15, 30, 60, and 120 min after active drug or placebo inhalation. The choice of drug vs. placebo on each visit will be random, and a double blind procedure will be implemented such that the participants and investigators will not be informed which study agent will be used on these visits. The inhaler used for visit 3 will be the alternate of the one that the subject is randomized to for visit 2.

Safety

There is minimal risk:

Echocardiography

No side effects have been reported.

Pulmonary function tests

There is little risk from spirometry. Some people may have some chest soreness or lightheadedness from the hard blowing. The chest soreness usually is short-lived, but can be treated with non-prescription pain relievers.

Inhaled Albuterol

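### The overall treatment effect is averaged over a pre-dose time level, which shrinks it to 4/5 of the post-dose mean difference; the plan does not say whether this effect or the undiluted interaction decides.

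*Combined protocol and SAP*

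**What the plan says.** The Statistical analysis section describes a within-participant factorial of treatment by "time post-treatment (pre-inhalation baseline, 15, 30, 60, 120min) as fixed within subject effects". The baseline is therefore one of five levels of a factor that the plan itself labels as post-treatment. The section plans "ANCOVA estimation of the main effects of treatment and time, as well as the 2-way interaction (treatment by time"), and continues: "In addition, ANCOVA analyses will be performed to examine treatment effects on the different outcomes". No covariate is named for either ANCOVA, no test is named as deciding, and significance is set at p < 0.05.

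Elsewhere, Targeted outcomes gives the outcome as "Change in MPAP, PVR after inhalation of" albuterol. The hypothesis, at the end of Background, is that "inhaled albuterol causes transient pulmonary vasodilation". Under Visit 2 and Visit 3, "The choice of drug vs. placebo on each visit will be random", with the other inhaler given at the third visit. On the expected time course, Targeted outcomes says that the albuterol response in healthy subjects had faded by 60 min. For long-acting agents in COPD, Background reports a fall in pressure that "lasted less than 180 min, with a trough minimizing between 15 min and 60 min". The Abstract says that significant lowering of MPAP and PVR could lead to a phase 2 trial. It gives 6 patients; Test subjects gives 10.

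**The concern.** The drug cannot have acted at the pre-inhalation measurement. Averaging that time point into an overall treatment effect pulls the estimate towards zero and adds the noise of one more measurement. If the main effect were the deciding result, the trial would give up power that it cannot easily spare at 6 to 10 participants. If the main effect were reported as the size of the effect, it would understate the average post-dose effect by 20%, and a phase 2 trial might be planned on that figure. Because the plan also contains an undiluted interaction test and does not rank the two, a reader cannot tell whether the dilution affects the conclusion.

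**Working it through.** The documents give no effect size, SD, correlation or power figure, so there is nothing of the plan's own to reproduce. Parts 1 to 3 are algebra. Part 4 is illustration.

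**1. The 4/5 factor.** Let d0, d15, d30, d60 and d120 be the mean albuterol-placebo differences at the five planned times. Write b = d0 and P = (d15 + d30 + d60 + d120)/4. In the balanced factorial the treatment main effect is

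M = (d0 + d15 + d30 + d60 + d120)/5 = (4P + b)/5.

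With random order and no carry-over, E[b] = 0, so E[M] = 0.8 × E[P] whatever the time course:

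| Effect at 15, 30, 60, 120 min (share of peak) | M | P | M/P |
|---|---|---|---|
| 1, 1, 1, 1 | 4/5 = 0.80 | 4/4 = 1.000 | 0.8 |
| 1, 1, 1, 0.5 | 3.5/5 = 0.70 | 3.5/4 = 0.875 | 0.8 |
| 1, 1, 0, 0 | 2/5 = 0.40 | 2/4 = 0.500 | 0.8 |

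A true P of 3 mmHg gives M = 4 × 3/5 = 2.4 mmHg. A chance b of 2 mmHg shifts M by 2/5 = 0.4 mmHg.

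**2. Precision.** Rescaled to estimate P, the main effect is M/0.8 = P + b/4, so

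Var(M/0.8) = Var(P) + Var(b)/16 + Cov(P,b)/2.

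This exceeds Var(P) unless the slope of P on b, Cov(P,b)/Var(b), is below -1/8. Two measurements on the same day would normally be positively related. Both tests have n-1 degrees of freedom, so the plain post-dose mean has more power than M in ordinary conditions.

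**3. When a baseline covariate helps.** Regress each participant's post-dose mean difference on the baseline difference; the intercept is the effect. Under normality,

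Var(adjusted)/Var(unadjusted) = (1 - r²)(n - 2)/(n - 3),

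which is below 1 only if r > 1/√(n - 2). That is 1/√8 = 0.35 at n = 10 and 1/√4 = 0.50 at n = 6.

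**4. Illustrative power.** Assumed, not documented: peak effect 5 mmHg, within-day SD 4, day-level SD 0 to 3, AR(1) correlation 0.3 to 0.6 (by time index or by clock time), two-sided 0.05. The early profile (1, 1, 0, 0) mimics the statement on healthy subjects. The sustained profile (1, 1, 1, 0.5) mimics the long-acting agents. Entries are power in %, with the range over the assumed settings.

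| Profile, n | Main effect, 5 levels | Post-dose mean | Post-dose mean, baseline-adjusted | Interaction, 5 levels, Greenhouse-Geisser |
|---|---|---|---|---|
| Early, 10 | 16-50 | 22-62 | 30-58 | 55-74 |
| Early, 6 | 10-28 | 13-36 | 16-29 | 22-36 |
| Sustained, 10 | 39-92 | 53-98 | 70-95 | 36-52 |
| Sustained, 6 | 22-65 | 30-78 | 37-66 | 14-23 |

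Three things follow within these assumptions.
- The unadjusted post-dose mean beat the five-level main effect in every setting.
- Against that unadjusted mean, the covariate changed power by -5 to +19 points at n = 10 and by -13 to +11 at n = 6.
- The interaction is the stronger test for the early profile at n = 10 and the weaker one for the sustained profile. If baseline were removed from the interaction as well, its power for the sustained profile at n = 10 would fall from 36-52% to 11-17%, because the change from baseline is most of its signal.

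**The case against.** The best defence is that the interaction is the natural test here. The outcome is a change after inhalation and the hypothesis is a transient effect. A change from baseline that differs by treatment is what a treatment-by-time interaction tests when baseline is a time level. On that reading the five-level layout is coherent and the main effect is incidental. Much of this stands: the interaction is undiluted, the same factorial can supply change-from-baseline contrasts, and the dilution does harm only through the main effect. But the interaction is a non-directional test on 4 degrees of freedom, and the plan does not say that it decides.

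It is also fair to object that the four-time post-dose mean is not always the better deciding test. For a response gone by 60 min it averages in two times with no effect and halves the peak. The documents do not settle which time course applies to these patients, so no single contrast can be prescribed from them.

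A reader might infer three stronger points that the documents do not support.
- *The trial's result will be 20% too small.* This holds only if the main effect is the reported effect size, which the plan does not say.
- *The error rate is inflated.* Accepting either the main effect or the interaction at p < 0.05 would give a type I error per outcome of about 8% (interaction corrected for sphericity) to 10-12% (uncorrected) at n = 10. The plan does not state such a rule.
- *The two tests will usually disagree.* How often exactly one is significant depends almost wholly on the assumed effect. At n = 10 it ranges from about 1% to 66% as the peak varies from 2 to 10 mmHg, so it is not a property of the plan.

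**Conclusion.** The concern holds in a limited form. The planned treatment main effect is (4P + b)/5. That is exact for complete data, and its expectation of 4/5 of P rests also on random order and no carry-over. The error is conservative: it costs power and can understate the effect, but it cannot create a false go-ahead. Its practical weight depends on the main effect being used to decide or to state the effect size, and the plan leaves that open. The firm gap is therefore that no deciding test and no ANCOVA covariate are named, while one of the candidate tests is needlessly diluted. This should be fixed but is not critical, since the Abstract treats a positive result only as a possible basis for phase 2. Confidence is high for the algebra. The power figures show direction only, because every variance and effect size behind them is assumed.

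**What to change.** Amend the Statistical analysis section as follows, before unblinding.

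1. Estimate the overall albuterol-placebo difference, with its 95% CI, from the 15, 30, 60 and 120 min values only.
2. Name that visit's pre-inhalation value as the ANCOVA covariate if about 10 participants complete. With about 6, use the unadjusted post-dose mean, which still removes the dilution. State this rule in advance.
3. Keep baseline as a time level only for the treatment-by-time interaction, with a sphericity correction, and for the change-from-baseline contrasts at each time.
4. Name which of these decides and justify it by the expected time course. The post-dose mean suits a sustained response; the interaction or an early-time contrast suits one that wanes by 60 min. Report the others as supportive.

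The cost is a few lines of wording, with no new data, visits or procedures. The covariate uses one degree of freedom, which is why it is conditional on the number completing. Choosing one deciding test means accepting less power if the response follows the other time course.

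### Two-visit crossover with no visit term named and equal sequences not required: a blocked order plus one visit term would cheaply guard against a lopsided split

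*Combined protocol and SAP*

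**What the plan says.** **Design.** Under Targeted outcomes, each patient is his or her own control and "the two treatments will be administered on different experiment days in random order". Under Procedures, Visit 2 and Visit 3, "The choice of drug vs. placebo on each visit will be random", and "The inhaler used for visit 3 will be the alternate of the one that the subject is randomized to for visit 2". So the only thing randomised is the order of the two treatments. No randomisation method, blocking or ratio of sequences is given.

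**Model.** The Statistical analysis section promises "ANCOVA estimation of the main effects of treatment and time, as well as the 2-way interaction (treatment by time"). Time is defined as "time post-treatment (pre-inhalation baseline, 15, 30, 60, 120min) as fixed within subject effects". It therefore means minutes within a visit and cannot stand in for visit 2 versus visit 3. The section continues "In addition, ANCOVA analyses will be performed to examine treatment effects on the different outcomes", without listing covariates.

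**Outcome.** Targeted outcomes names "Change in MPAP, PVR after inhalation", with a pre-dose measurement on each day.

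**Sample size.** The Abstract says 6 patients; Test subjects says 10.

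**The concern.** In a two-period crossover, a systematic difference between the first and second treatment visits is usually handled in two ways: by balancing the two orders and by fitting a period term. Neither is written here. If more patients receive albuterol first than second, part of any visit effect on the post-dose response is attributed to albuterol. If the orders happen to be equal, the visit effect drops out of the estimate but, with no term to absorb it, inflates the residual variance.

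With 6 or 10 patients an uneven split is not rare. The study will be run once, and its result is meant to inform whether a phase 2 trial follows. Unbiasedness over hypothetical repetitions is limited comfort for that single estimate.

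**Working it through.** The protocol gives no power, effect size or SD, so there is no stated figure to reproduce.

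**Inputs from the protocol:** n = 10 or 6, significance level 0.05, two treatments in random order.

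**Assumptions:** two-sided testing; simple 1:1 randomisation of the order; one summary treatment difference per patient; visit effects v of 0.25, 0.5 and 1 SD of that within-patient difference; treatment effect τ of 1 SD for power.

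**Model.** For patient i the difference (albuterol minus placebo) in change from baseline is dᵢ ~ N(τ + sᵢv, 1), with sᵢ = +1 or −1 by order. With n₁ and n₂ patients in the two orders, the mean of dᵢ is τ + rv, where r = (n₁ − n₂)/n. So |r| is the share of the visit effect that enters the treatment difference.

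**What cancels.** A shift that moves every reading on one day by the same amount cancels from change from that day's baseline, and from treatment-by-time. It reaches only the treatment main effect on raw values, which pools in the pre-dose reading. For the stated outcome, v is a visit difference in the post-dose change.

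**Type I error without a visit term.** The squared paired t is doubly noncentral F(1, n−1), with numerator noncentrality n(τ + rv)² and denominator noncentrality nv²(1 − r²); here τ = 0.

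| Split | Probability | Share of v | v = 0.25 | v = 0.5 | v = 1 |
|---|---|---|---|---|---|
| 5:5 | 252/1024 = 24.6% | 0 | 4.4% | 3.0% | 0.7% |
| 6:4 | 420/1024 = 41.0% | 20% | 4.6% | 3.7% | 1.7% |
| 7:3 | 240/1024 = 23.4% | 40% | 5.3% | 6.1% | 6.4% |
| 8:2 | 8.8% | 60% | 6.6% | 10.6% | 20.1% |
| 3:3 | 20/64 = 31.3% | 0 | 4.5% | 3.1% | 0.8% |
| 4:2 | 30/64 = 46.9% | 33% | 4.8% | 4.2% | 2.5% |
| 5:1 | 18.8% | 67% | 5.9% | 8.2% | 13.1% |

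A split of 7:3 or worse has probability (240 + 112)/1024 = 34.4%; 5:1 or worse has 14/64 = 21.9%. Averaged over all splits, type I error is 5.0%, 5.0% and 5.2% with 10 patients, and 5.0%, 5.1% and 5.5% with 6.

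**Power at τ = 1.** With the term, the test is noncentral t on n − 2 df, with SE = √((1/n₁ + 1/n₂)/4), and does not depend on v.

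| | v = 0 | v = 0.25 | v = 0.5 | v = 1 |
|---|---|---|---|---|
| n = 10, simple order, no term | 0.803 | 0.779 | 0.711 | 0.500 |
| n = 10, 5:5, no term | 0.803 | 0.783 | 0.720 | 0.482 |
| n = 10, 5:5, with term | 0.791 | 0.791 | 0.791 | 0.791 |
| n = 6, simple order, no term | 0.507 | 0.484 | 0.423 | 0.270 |
| n = 6, 3:3, no term | 0.507 | 0.479 | 0.404 | 0.195 |
| n = 6, 3:3, with term | 0.463 | 0.463 | 0.463 | 0.463 |

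At equal sequences, the term gains power above v of about 0.20 SD (5:5) or 0.32 SD (3:3).

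**Term without blocking.** The variance of the estimate is multiplied by n²/(4n₁n₂): 100/84 = 1.19 at 7:3, 100/64 = 1.56 at 8:2, 36/20 = 1.80 at 5:1. Power at τ = 1 is 0.774 at 6:4, 0.719 at 7:3 and 0.422 at 4:2. At 10:0 or 6:0, treatment and visit cannot be separated.

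**The case against.** The strongest reply is that no error in the plan has been shown and that the threat is narrow. Four parts of it stand.

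- The documents give no evidence of a visit effect, and they standardise the visits: "Visits 2 and 3 will commence about 9am", background oral vasodilators are continued, imaging follows a fixed rest period, and treatment is double blind. This makes a visit effect less likely without excluding it. The 0.5 and 1 SD columns are illustrations.
- Because the outcome is a change from same-day baseline, ordinary day-to-day shifts cancel. Only a visit difference in the post-dose course, common to all patients, matters.
- Blocking or visit adjustment may be intended. ANCOVA is named with its covariates unlisted. What can be said is that neither is written.
- The figures use one summary difference per patient and a paired test. They do not give type I error or power for the planned treatment-by-time interaction.

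The reply does not remove the point. With so few patients, an uneven split under simple randomisation is common, and the protection costs little with 10.

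A reader might infer that the missing visit term biases the study or inflates its false-positive rate. The documents do not support that. At the more likely splits (5:5 or 6:4, 66%; 3:3 or 4:2, 78%) the plain test is conservative. Marked inflation needs a split of 8:2 or 5:1 or worse together with a visit effect of about 0.5 SD or more.

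**Conclusion.** The point holds as a low-severity, inexpensive improvement. The protocol names no visit term and does not require equal sequences. Under assumed simple randomisation, roughly one trial in three with 10 patients, or one in five with 6, would have a split at which a substantial share of any post-dose visit effect sits in the treatment difference.

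Two stronger inferences should be resisted. First, the fix does not always improve precision. With no visit effect, the critical t rises from 2.262 to 2.306 with 10 patients (interval 1.9% wider) and from 2.571 to 2.776 with 6 (8.0% wider). The break-even visit effect also moves with the assumed treatment effect: over 0.5 to 1.5 SD it runs from about 0.14 to 0.235 SD at 5:5, and from about 0.225 to 0.38 SD at 3:3. The documents give no figure for either effect. Second, blocking alone is not a free half-measure. Balance moves the visit effect into the error variance, so the test becomes conservative and power can fall below that of simple randomisation, most visibly with 6 patients.

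The case for the fix is clear at 10 patients and closer at 6, where even a 0.25 SD visit effect leaves it slightly behind simple randomisation without the term (0.463 against 0.484).

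**What to change.** First reconcile the sample size between the Abstract and Test subjects, because the cost of the visit term depends on it. Then make both changes together:

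1. Allocate the two sequences in equal numbers from a concealed blocked list that closes at the final sample size (5:5 for 10 patients, 3:3 for 6), and state the method under Procedures.
2. In the Statistical analysis section, analyse change from same-visit baseline for each outcome, with visit (2 or 3) as one fixed effect. A visit-by-time term in the full repeated-measures model can be an optional sensitivity analysis.

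Do not adopt the blocked list without the term.

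The cost is a randomisation list, a clearer specification of the change analysis, and one degree of freedom. No extra patients, visits or measurements are needed. Withdrawals, which the protocol allows, can undo exact balance: with no visit effect and a 1 SD treatment effect, the term changes power from 0.748 to 0.725 at 5:4 and from 0.401 to 0.333 at 3:2.
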